The use of CPAP for treatment of OSA should be exempt from the requirements of 21 CFR Part 812 because this represents a medically cleared device (ResMed AirSense 11 AutoSet: K203126), used for its labeled indication (i.e., treatment of OSA). The UW Institutional Review Board (IRB) has assigned a no more than minimal risk status in similar studies.^{26,65,66} CPAP is a safe treatment. The most common side effects of CPAP include mask-related discomfort; dry eyes, nose, mouth and/or throat; nasal congestion; stomach bloating; and difficulty falling or staying asleep. These are all non-serious. Skin irritation related to the mask interface, or rarely skin allergy can occur. We will minimize these risks by having a variety of mask and nasal pillow interfaces, and offering multiple options. Respiratory therapists and sleep technicians will assist with mask fit and troubleshoot any discomfort during the IPR hospitalization. For all participants, we will make use of

respiratory therapy expertise during IPR and provide information for DME-support after IPR discharge to make CPAP as comfortable as possible, which would be covered by the study. For persistent issues related to CPAP, the study team may ask the participant if he/she would like a referral to the local sleep medicine clinic, that would not be covered by the study.

Protection Against Risk

Patients will be excluded from the study after enrollment if they are found to have central sleep apnea ($\geq 50\%$ of apneas related to central events) or no evidence of OSA (respiratory event index < 5 per hour) on the Nox T3s sleep recording. In such case, the results of the sleep apnea testing will be given to the participant and the IPR clinical team caring for the patient. Either a sleep technologist or respiratory therapist, depending on randomization assignment, will be involved in mask fitting to assure appropriate size selection. For all participants, the respiratory therapists or sleep tech will troubleshoot any CPAP issues during ideally each night of inpatient use. Participants will also be offered a variety of masks/interfaces to facilitate comfort. Heated humidification will be used to reduce mucosal dryness and maximize adherence. The consent form provides information about withdrawal of study participants for pregnancy and the need to discuss this topic, should it arise, with study staff and the participant's physician. This should be rare given our stroke population. Participants will be cautioned not to drive when sleepy, though sleepiness is not a prominent feature of post-stroke OSA.⁶⁷⁻⁶⁹

Regarding loss of privacy or confidentiality from data gathered from the Nox T3s sleep apnea test, CPAP use or MET interviews, all participant health information and personal identifiable information is kept confidential on ResMed AirView, ResMed myAir and Lyssn cloud-based applications. Also, the privacy policy from ResMed, and Lyssn will be provided to participants at the time of enrollment. The informed consent document will outline the use of these applications including the need to share identifiers with ResMed as part of this use - a procedure often done as part of routine medical care related to CPAP. Regarding risks of the questionnaires or MET counseling sessions, participants will be given the option to stop answering questionnaires or counseling or to take a break if they become physically tired or emotionally upset. No particularly sensitive topics are planned for discussion. Participants will be assured that they are not required to answer a question if a particular question makes them uncomfortable and can also withdraw their study participation at any time.

The data collection process or MET session will be postponed and rescheduled at another time if needed and if agreeable to the participant. Our study staff will undergo strict training in the proper way to conduct interviews with personal health information, including HIPAA and Good Clinical Practice (GCP) training. We protect Protected Health Information (PHI) with all of our efforts. Study participants' identification numbers will be used on forms rather than names.

Vulnerable Subjects

No prisoners, children, or pregnant women will be enrolled. Pregnancy is an exclusion criterion because of potential safety concerns for the fetus and mother related to untreated OSA. Women of child-bearing potential will be included. Participants who become pregnant will be withdrawn from the study. This should be uncommon given the stroke population. Pregnancy testing is considered part of routine care for stroke patients.

Potential Benefits

Potential direct benefits to research study participants include sleep apnea testing using a portable device, education regarding OSA after stroke, and CPAP therapy for all those who meet the study's OSA treatment criteria. Both the screening sleep apnea study and the initiation of CPAP are rarely performed in the inpatient stroke setting due to logistic challenges and clinical equipoise related to the potential benefits of early CPAP treatment. Benefits to the intervention may include improved adherence to CPAP therapy, improved stroke recovery or secondary stroke prevention and better overall health outcomes. In regards to indirect benefits, the project has the potential to generate important new and much-needed information about improving adherence to CPAP therapy and the treatment of post-stroke OSA. The no more than minimal risks associated with this study are reasonable considering the significant potential direct and indirect benefits.

Enrolled stroke participants will be compensated for their time with \$25 for completion of the outcome assessment at 3 months.

AE monitoring and reporting

Given the no more than minimal risk nature of the study, [name] will be responsible for monitoring the safety of participants. Given the risks, only serious adverse events that are definitely, possibly, or have a reasonable possibility of being related to a study procedure will be reported to the IRB. Standard definitions of serious adverse events, relatedness, and seriousness will be used. Standard reporting scheduled will be applied.

Statistical analysis

The primary endpoint is the themes related to acceptability, feasibility, and appropriateness of the behavioral adherence intervention based upon participant and CPAP partner feedback during the semi-structured interviews. The secondary endpoint is 3-month average nightly CPAP usage.

Demographic and stroke- or sleep-related factors associated with mean CPAP use will be assessed using t-tests for dichotomous variables and linear regression for continuous variables. Additional post-hoc analysis of race/ethnicity may be completed.

Introductory Pamphlet (to be edited)

NIH Stroke Scale

NIH Stroke Scale Item	Function	Scores	Score
1a. Level of Consciousness (Alert, Drowsy, etc.)	Alert Drowsy Stuporous (requires repeated stimuli) Comatose (reflex responses only)	0 1 2 3	
1b. LOC Questions (Ask month, age)	Both correct One Correct Both Incorrect, unable to answer	0 1 2*	
1c. LOC Commands (Open, close eyes, make fist, let go)	Obeys both correctly Obeys one correctly Both Incorrect, unable to perform*	0 1 2*	
2. Best Gaze (Eyes open-patient follows examiner's finaer or race)	Normal Partial gaze palsy (for coma see Forced deviation Note 2 below)	0 1 2	
3. Visual (Introduce visual stimulus threat to patient's visual field quadrants)	No loss Partial hemianopia (for coma see Complete hemianopia Note 3 below) Bilateral hemianopia	0 1 2 3	
4. Facial Palsy (Show teeth, raise eyebrows and squeeze eyes shut)	Normal Minor asymmetry Partial (lower face paralysis) Comotole*	0 1 2 3*	
5a. Motor Arm-Left (Elevate extremity 90 degrees When sitting and score drift/movement)	No drift Drift Some effort against gravity No effort against gravity No movement"	0 1 2 3 4**	
5b. Motor Leg-Left (Elevate extremity 30 degrees When lying down and score drift/movement)	No drift Drift Some effort against gravity No effort against gravity No movement*	0 1 2 3 4*	
6a. Motor Arm-Right (Elevate extremity 90 degrees When sitting and score drift/movement)	No drift Drift Some effort against gravity No effort against gravity No movement'	0 1 2 3 4*	
6b. Motor Leg-Right (Elevate extremity 30 degrees When lying down and score drift/movement)	No drift Drift Some effort against gravity No effort against gravity No movement'	0 1 2 3 4*	
7. limb Ataxia (Finger-Nose, heel down shin)	Absent' Present in upper or lower Present in both	0* 1 2	
8. Sensory (Pin prick to face, arm, trunk, and leg comoare side to sidel	Normal Partial Loss Dense Loss*	0 1 2*	
9. Best Language (Name items, describe picture and read sentences)	No aphasia Mild-moderate aphasia Severe aphasia (see Intubated and Alert notes) Mute*	0 1 2 3*	
10. Dysarthria (Evaluate speech darity by patient repeatinga listed words)	Normal articulation if appropriate) Mild-moderate slurring Severe. nearly unintelliaible or worse	0 1 2*	
11. Extinction and Inattention (Use information from prior testing to identify nelect or double simultaneous stimuli testinal	No neglect Partial neglect Profound Neolecr	0 1 2*	
NIH Stroke Scale Total			

* assign this score 1f patient comatose or unresponsive

Note 2: perform oculocephalic testing to determine score if comatose, absent oculocephalic reflex leads to score of 2

Note 3: determine via visual threat if comatose, no response leads to score of 3

Intubated and Alert: for item 9, make best guess and score; for item 10, untestable so score 0

MRS-9Q

Question 1: Do you have any symptoms that are bothering you? YES | NO

Question 2: Are you able to do the same work as before? YES | NO

Question 3: Are you able to keep up with your hobbies? YES | NO

Question 4: Have you maintained your ties to friends and family? YES | NO

Question 5: Do you need help making a simple meal, doing household chores, or balancing a checkbook? YES | NO

Question 6: Do you need help with shopping or traveling close to home? YES | NO

Question 7: Do you need another person to help you walk? YES | NO

Question 8: Do you need help with eating, going to the toilet, or bathing? YES | NO

Question 9: Do you stay in bed most of the day and need constant nursing care? YES | NO

Pre-stroke Berlin (baseline only) – 10 items

Read to participant: “Please answer the following set of questions as you would have BEFORE your recent stroke.”

1. Do you snore?

0 = No (Go to 6.2)

1 = Yes

80 = Don't know (Go to 6.2)

1a. Would you say your snoring is:

1 = Slightly louder than breathing

2 = As loud as talking

3 = Louder than talking

4 = Very loud; can be heard in adjacent room

80 = Don't know

1b. How often do you snore?

1 = Nearly every day

2 = 3-4 nights per week

3 = 1-2 nights per week

4 = 1-2 nights per month

5 = Never/nearly never

80 = Don't know

1c. Has your snoring ever bothered other people?

0 = No

1 = Yes

80 = Don't know

2. Has anyone noticed that you quit breathing during your sleep?

0 = No (Go to 6.3)

1 = Yes

80 = Don't know (Go to 6.3)

2a. How often would you say you quit breathing during your sleep?

1 = Nearly every day

2 = 3-4 times a week

3 = 1-2 times a week

4 = 1-2 times a month

5 = Never/nearly never

80 = Don't know

3. How often do you feel tired or fatigued after your sleep?

1 = Nearly every day

2 = 3-4 times a week

3 = 1-2 times a week

4 = 1-2 times a month

5 = Never/nearly never

80 = Don't know

4. During your wake time, how often do you feel tired, fatigued, or not up to par?

1 = Nearly every day

2 = 3-4 times a week

3 = 1-2 times a week

4 = 1-2 times a month

5 = Never/nearly never

80 = Don't know

5. Have you ever nodded off or fallen asleep while driving a vehicle?

0 = No (Go to 6.6)

1 = Yes

80 = Don't know (Go to 6.6)

5a. How often would you say you nod off or fall asleep while driving a vehicle?

1 = Nearly every day

2 = 3-4 times a week

3 = 1-2 times a week

4 = 1-2 times a month

5 = Never/nearly never

80 = Don't know

6. What is your height?

____feet ____inches

7. What is your weight?

____lbs

8. Do you have high blood pressure?

RESPONSE OPTIONS: yes, no, don't know

Motivation to Use CPAP Scale (**baseline only**) – **9 items** - visit 8 (Day 5-7 and after 3-day ST visits)

Now I'm going to ask you 9 questions about what motivates you to use CPAP.

1. I use the CPAP treatment because it makes me feel good.	Strongly agree 5	Agree 4	Undecided 3	Disagree 2	Strongly disagree 1
2. I use the CPAP treatment because I want to avoid having apneas.	Strongly agree 5	Agree 4	Undecided 3	Disagree 2	Strongly disagree 1
3. I use the CPAP treatment because I want to feel more alert.	Strongly agree 5	Agree 4	Undecided 3	Disagree 2	Strongly disagree 1
4. I use the CPAP treatment because it feels important to use the CPAP.	Strongly agree 5	Agree 4	Undecided 3	Disagree 2	Strongly disagree 1
5. I use the CPAP treatment because my health is important to me.	Strongly agree 5	Agree 4	Undecided 3	Disagree 2	Strongly disagree 1
6. I use the CPAP treatment because it feels good to use CPAP.	Strongly agree 5	Agree 4	Undecided 3	Disagree 2	Strongly disagree 1
7. I use the CPAP treatment because other people say I have to.	Strongly agree 5	Agree 4	Undecided 3	Disagree 2	Strongly disagree 1
8. I use the CPAP treatment because the personnel say I have to.	Strongly agree 5	Agree 4	Undecided 3	Disagree 2	Strongly disagree 1
9. I use the CPAP treatment because I have to.	Strongly agree 5	Agree 4	Undecided 3	Disagree 2	Strongly disagree 1

Prestroke sleep duration & Quality (baseline in reference to pre-stroke state)

Sleep duration:

During the month prior to the stroke, excluding naps, how many hours of actual sleep did you get at night (or day, if you work at night) on average?

RESPONSE OPTIONS: < 6 hours per night, 6-8 hours per night, > 8 hours per night

Sleep quality:

During the month prior to your stroke, how would you rate your sleep quality overall?

RESPONSE OPTIONS: 1 = excellent, 2 = very good, 3 = good, 4 = fair, 5 = poor

Prestroke sleep duration & Quality (90 day)

Sleep duration:

During the past month, excluding naps, how many hours of actual sleep did you get at night (or day, if you work at night) on average?

RESPONSE OPTIONS: < 6 hours per night, 6-8 hours per night, > 8 hours per night

Sleep quality:

During the past month, how would you rate your sleep quality overall?

RESPONSE OPTIONS: 1 = excellent, 2 = very good, 3 = good, 4 = fair, 5 = poor

After Nox T3 sleep apnea test

Was the T3 qualifying for CPAP treatment (REI ≥ 5 and CAI was $<50\%$ of REI)?

RESPONSE OPTIONS: yes, no, sufficient data not obtained

If yes,

Did the participant try CPAP for at least one night?

RESPONSE OPTIONS: yes, no

Participant phone number:

Participant email:

Participant address:

Did the participant identify a CPAP partner?

RESPONSE OPTIONS: yes, no

If yes,

CPAP partner name

CPAP partner phone number

7 adverse symptoms of CPAP (after night 1, night 2 and night 3 of using CPAP)

“Did you have problems with CPAP last night?”

No **Yes**

“We would like you to answer yes or no to some **side effects** of CPAP that people may experience.”

List of 7 adverse events or problems associated with CPAP use

Patient receives a score of one point for the presence of any complaints within each category, producing a total possible side effect score of seven points.

Mouth dryness

Nasal symptoms

Eye problems

Claustrophobia

Noise problems

Facial soreness or skin irritation from the mask

Mask fit or leak problems (i.e. trouble keeping mask in place, air leaks or difficulty putting the mask on)

“Some other side effects that people may experience include: dry nose or throat, headache, sore throat, jaw pain, waking up frequently, stomach upset, or increased saliva. Have you had any of these side effects?”

Asked of CPAP Partner

Short-form 7-item Zarit Burden Interview (discharge, 90 day) measured on a 5-point Likert scale from 0 (never) to 4 (nearly always)

INSTRUCTIONS: The following is a list of statements, which reflect how people sometimes feel when taking care of another person. After each statement, indicate how often you feel that way; never, rarely, sometimes, quite frequently, or nearly always. There are no right or wrong answers.

1. Do you feel you do not have enough time for yourself?

RESPONES OPTIONS: 0: NEVER 1: RARELY 2: SOMETIMES 3: QUITE FREQUENTLY 4: NEARLY ALWAYS

2. Do you feel stressed between caring and meeting other responsibilities?

RESPONES OPTIONS: 0: NEVER 1: RARELY 2: SOMETIMES 3: QUITE FREQUENTLY 4: NEARLY ALWAYS

3. Do you feel your relative affects your relationship with others in a negative way

RESPONES OPTIONS: 0: NEVER 1: RARELY 2: SOMETIMES 3: QUITE FREQUENTLY 4: NEARLY ALWAYS

4. Do you feel strained when are around your relative?

RESPONES OPTIONS: 0: NEVER 1: RARELY 2: SOMETIMES 3: QUITE FREQUENTLY 4: NEARLY ALWAYS

5. Do you feel your health has suffered because of your involvement with your relative?

RESPONES OPTIONS: 0: NEVER 1: RARELY 2: SOMETIMES 3: QUITE FREQUENTLY 4: NEARLY ALWAYS

6. Do you feel you have lost control of your life since your relative's illness?

RESPONES OPTIONS: 0: NEVER 1: RARELY 2: SOMETIMES 3: QUITE FREQUENTLY 4: NEARLY ALWAYS

7. Overall, how burdened do you feel in caring for your relative?

RESPONSES OPTIONS: 0: NEVER 1: RARELY 2: SOMETIMES 3: QUITE FREQUENTLY 4:
NEARLY ALWAYS

REFERENCES

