Nox T3s data will be uploaded for review by a scoring team at Elite Sleep Professionals, or similar organization of registered polysomnographic technologists. The sleep apnea tests will not be reviewed by a physician. Study participants who are eligible for the CPAP adherence intervention will not be told of the severity of OSA until completion of study participation so that any decision to adhere to CPAP is not influenced by OSA severity from a single-night HSAT, which typically underestimates the disease severity.³⁸⁻⁴⁰ Nox T3s reports will be provided to the participant and the clinical team at the time the participant exits participation in this study. Based upon prior studies in this population^{4-6 17} we anticipate that about 20% of the 60 participants with completed OSA tests may be excluded based on these criteria, yielding approximately 48 participants for the Aim 1 adherence program adaptation.

Existing SCOUTS2 adherence intervention, implemented for participants

Participants who meet criteria for a diagnosis of OSA will be set up with CPAP on the next available night after the HSAT by study staff led by the study's sleep technologist, who will provide mask fitting and CPAP exposure during the daytime prior to the 1st night of CPAP use. The CPAP device (AirSense™ 11 AutoSet, ResMed) includes an auto-titrator that can adjust the delivered pressure between 4 to 20 cm of water to eliminate obstructive events. Pressure settings may be narrowed. All Aim 1 participants may receive 3 basic supportive treatments to approximate the care provided after a sleep clinic or in-hospital diagnosis of OSA: 1) education on OSA and the importance of CPAP treatment for improved sleep and vascular health; 2) standard inpatient CPAP support from respiratory therapy and IPR nurses for mask placement and adjustments; and 3) outpatient access to a national durable medical equipment (DME) company, for issues that may arise with CPAP at home. Participants may also receive 3 behavioral adherence interventions:

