(i) CPAP technical support: Initial mask fitting will be completed by the study's sleep technologist on the IPR unit rather than by respiratory therapists, if possible. The study's sleep technologist will initially ensure adequate mask fit without air leak, trial different CPAP mask interfaces for patient comfort and provide education or adjustments to address adherence issues.⁴¹ A member of the SCOUTS3 team led by the study's sleep technologist may then meet ideally daily with participants over the first three days of initiating CPAP to assess perception of treatment and symptom-related treatment response;^{42,43} complete a 7-item questionnaire of common adverse symptoms associated with CPAP (appended);⁴⁴ make mask type/size or device adjustments, as needed; and provide training to participants and CPAP partners to improve skills involved with mask placement and device maintenance. For participants with non-acceptance of CPAP over the first night, a standardized desensitization program may be implemented by the sleep technologist. Persistent problems with CPAP use, mask fit, or high residual respiratory events may be discussed between the sleep technologist and Co-I [name], a board-certified sleep medicine physician.

(ii) MET with individualized verbal and written feedback: In-person MET sessions during IPR and telephone sessions after IPR discharge will also be completed by a sleep coach. The in-person MET sessions will occur typically within 3 days of starting CPAP and again after about 3 to 5 days if the participant remains on IPR. The 1st in-person MET session will focus on subjective assessment of CPAP use, barriers and facilitators of use, assessment of motivation and confidence for use, decisional balance and feedback. The 2nd MET session will focus on subjective appraisals of CPAP adherence, reinforcement of changes with treatment, and review of treatment goals. The post-discharge MET phone sessions will begin approximately two weeks after discharge, then monthly during the 3 months of CPAP therapy and will last approximately 30-60 minutes. Consistent with prior research in stroke patients on the dose of MET needed, the goal will be to deliver a total of 4 hours of MET counseling over the 3 months of CPAP therapy.^{45,46} In the spirit of MET, the participants will dictate the pace of the sessions. We may alter the frequency, duration, and content of the sessions based on participant feedback.

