For aphasic participants, the sleep coach will use published recommendations to adapt MET sessions for people with stroke-related aphasia, including strategies to enhance language comprehension and facilitate

expression⁴⁷⁻⁴⁹ and patient-specific strategies recommended by the study participant's speech-language pathologists on the IPR unit. Patients with more severe aphasia with complete incomprehension are not typically admitted to IPR. The MET for aphasic participants will include two face-to-face sessions during IPR, each lasting about 30 to 60 minutes, and one ~20-minute phone session with inclusion of the CPAP partner, when possible. Face-to-face sessions will incorporate MET components used in non-aphasic participants but will focus on information exchange through visual aids, exploring potential barriers to CPAP use through enhanced communication and goal setting.⁵⁰ MET sessions may be bolstered by individualized written and visual feedback regarding the OSA testing, potential vascular consequences, and CPAP download data illustrating the effectiveness of treatment in reducing respiratory events.

Fidelity for the MET sessions will be evaluated in multiple ways. Some MET sessions will be recorded, uploaded for processing, and reviewed via the cloud-based and HIPAA-compliant Lyssn platform, which supports training and quality assurance by providing automated transcription and fidelity feedback from a session recording. The recordings are processed through the system's artificial intelligence analytics tool and automatically transcribed via speech-to-text transcription. The platform will produce reports of each session, including general and specific metrics for MET. The sessions will be evaluated through the Lyssn platform and feedback reports will be provided to the sleep coach. Consultants, [name] and [name], may also review ~20% of the counseling sessions for non-aphasic participants utilizing a MET checklist to provide feedback to the sleep coach via quarterly virtual meetings.²⁰ Co-I [name], who has adapted motivational counseling to improve adherence to therapy in other populations,⁵¹ may review ~20% of the recordings of aphasic participants utilizing a modified MET checklist.

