- Interview with participants and, if available, CPAP partners after 3 days to evaluate impressions of CPAP technical support
- Interviews will last approximately 30 minutes

Visit 9 (in-hospital and in-person during inpatient rehabilitation)

- An in-person Motivational Enhancement Therapy (MET) session will occur by a trained sleep coach within the first the first week of starting CPAP and again within a week if the participant remains on IPR. Initial session will last approximately 60 minutes for non-aphasic participants.
- For aphasic participants, the sleep coach will use published recommendations to adapt MET sessions for people with stroke-related aphasia, including strategies to enhance language comprehension and facilitate expression and patient-specific strategies recommended by the study participant's speech-language pathologists on the IPR unit. These sessions will focus on information exchange through visual aids, exploring potential barriers to CPAP use through enhanced communication and goal setting and will last 30-60 minutes
- An in-person or phone MET session will also be conducted with a CPAP partner, when available. With participant permission, MET sessions for CPAP partners will focus on the OSA diagnosis, standard therapy for OSA and ways the CPAP partner can provide support for the participant

Visit 10 (in-hospital and in-person during inpatient rehabilitation)

- A second in-person Motivational Enhancement Therapy (MET) session will occur within a week if the participant remains on inpatient rehabilitation.

Visit 11 (in-hospital and in-person during inpatient rehabilitation)

- The research coordinator will meet with participants to assist in registering for the mobile health (mHealth) ResMed myAir app, demonstrate use of the app, and provide increased support to participants if needed, including those with deficits related to dexterity, aphasia and cognition. Increased efforts will be made with aphasic participants or those with other cognitive or dexterity deficits, including frequent coaching during IPR, utilizing patient-specific strategies recommended by the IPR unit's speech-language pathologists and working with caregivers when possible.

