- Participants limited by dexterity issues will be trained to use a stylus. Screen zoom features will be implemented if the participant has difficulty seeing due to presbyopia. Tablets or internet card-enabled devices will be provided to those without access to smartphone, tablet or home internet service.

Visit 12 (in-hospital during inpatient rehabilitation)

- At the end of inpatient rehabilitation, a brief (~10 minutes) set of questionnaires and assessments will be repeated for baseline stroke severity and functional disability by a certified investigator.
- Interview with participants and, if available, CPAP partners will be conducted to evaluate impressions of the inpatient MET sessions and mHealth interventions

Visit 13-14 (by phone to participant's home or other facility after discharge from inpatient rehabilitation)

- A post-discharge MET phone sessions will occur approximately two weeks after discharge from the inpatient rehabilitation unit and last approximately 30-60 minutes.
- A repeat and final MET phone session will occur approximately 1 months after the prior one and will last approximately 30-60 minutes

Visit 15-16 (by phone to participant's home or other facility after discharge from inpatient rehabilitation)

- The research coordinator will call participants approximately monthly after discharge from the inpatient rehabilitation unit (on 2 occasions over the 3-month study treatment period) to encourage use and resolve problems with therapy.

Visit 17 (by phone to participant's home or other facility after discharge from inpatient rehabilitation)

- After approximately 90 ± 14 days from enrollment, a certified investigator will repeat questionnaires and assessments (~10 minutes) for baseline stroke severity and functional disability.
- At the end of the 3-month treatment period, a repeat interview with participants and, if available, CPAP partners will be conducted to evaluate impressions of the outpatient MET sessions and mHealth interventions

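### Do the differing MET call schedules for aphasic participants, and the 4-hour MET goal, require a change to the plan?

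*Combined protocol and SAP*

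**What the plan says.** The MET component is item (ii) under the heading on the existing SCOUTS2 adherence intervention. That section introduces the components permissively: "Participants may also receive 3 behavioral adherence interventions". The general MET paragraph describes in-person sessions during inpatient rehabilitation (IPR), the second only if the participant is still an inpatient. Phone sessions of about 30-60 minutes follow, the first some two weeks after discharge and the rest monthly, with no number given. It adds that "the goal will be to deliver a total of 4 hours of MET counseling over the 3 months of CPAP therapy", and then: "We may alter the frequency, duration, and content of the sessions based on participant feedback".

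The next paragraph turns to aphasic participants and gives their MET as "two face-to-face sessions during IPR, each lasting about 30 to 60 minutes, and one ~20-minute phone session", with the CPAP partner included where possible.

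The visit list, headed as an overview of design and methods, covers the same ground by visit:

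- Visit 9, non-aphasic: "Initial session will last approximately 60 minutes for non-aphasic participants".
- Visit 9, aphasic: the description ends "exploring potential barriers to CPAP use through enhanced communication and goal setting and will last 30-60 minutes".
- Visit 10: a second in-person session if the participant is still on IPR; no length is stated.
- Visits 13-14: "A post-discharge MET phone sessions will occur approximately two weeks after discharge from the inpatient rehabilitation unit and last approximately 30-60 minutes", and then "A repeat and final MET phone session will occur approximately 1 months after the prior one and will last approximately 30-60 minutes". Aphasia is not mentioned.

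Just before the section on adaptation and refinement, the protocol says that components not delivered are expected and will not be reported as deviations.

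**The concern.** Read side by side, the two texts give the same aphasic participants different outpatient MET: one short call or two longer ones. The visit list treats aphasic participants separately at Visits 9 and 11, so its silence at Visits 13-14 could be taken to mean that those calls apply to everyone. Nothing says which text governs.

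The 4-hour goal makes this look worse. It names no subgroup, and the sessions listed for aphasic participants fall well short of it even at full length. Aim 1a gives language dysfunction as one reason for adapting the package, and the Visit 17 interview asks about outpatient MET. If the starting schedule is unclear for the group whose needs motivate the adaptation, feedback from that group could be harder to interpret.

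**Working it through.** **Inputs.** Session numbers and lengths come from item (ii) and its aphasia paragraph, and from Visits 9, 10, 13 and 14. The goal is 4 × 60 = 240 min. The protocol itself gives no sum of session minutes. Visit 10 has no stated length, so 30-60 min is assumed for it.

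**Totals** = sum of (sessions × minutes), lower to upper bound:

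| Reading | Calculation | Minutes |
|---|---|---|
| Aphasia text, both in-person sessions | 2×30+20 to 2×60+20 | 80-140 |
| Aphasia text, one in-person session | 30+20 to 60+20 | 50-80 |
| Visit list read for aphasic, with Visit 10 | 4×30 to 4×60 | 120-240 |
| Visit list read for aphasic, without Visit 10 | 3×30 to 3×60 | 90-180 |
| Visit list, non-aphasic, with Visit 10 | 60+30+2×30 to 60+60+2×60 | 150-240 |
| Visit list, non-aphasic, without Visit 10 | 60+2×30 to 60+2×60 | 120-180 |
| General MET text, assuming three calls and two in-person sessions of 30-60 min | 5×30 to 5×60 | 150-300 |

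**Call time alone.** About 20 min against 2×30 = 60 to 2×60 = 120 min: a gap of 40-100 min, or a ratio of 3 to 6.

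**Against the goal.** 80/240 = 33% and 140/240 = 58%, so the aphasia text is 160 to 100 min short. Non-aphasic participants on the visit list reach 240 min only if Visit 10 takes place and every session runs to its upper bound. The 4 hours is therefore tight for everyone on that list, which fits its description as a goal.

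**Is it a contradiction?** The shortfall conflicts with the goal only if two things hold: the goal covers aphasic participants, and the aphasia paragraph is a complete list. The documents state neither. The call schedules oppose each other only if Visits 13-14 are meant to override the aphasia paragraph, which is also not stated. One smaller difference lies in the in-person part: the lengths agree, but the aphasia paragraph gives two sessions without condition, while the general text and Visit 10 make the second depend on still being an inpatient.

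**Does it reach the analysis?** The Statistical analysis section makes themes from the participant and CPAP-partner interviews the primary endpoint and 3-month average nightly CPAP use the secondary. Planned MET minutes enter neither. The analyses of factors associated with mean CPAP use are t-tests and linear regressions, and MET dose is not named in them. The figures of 60 enrolled and about 48 continuing come from the expected 20% exclusion after sleep testing (60 × 0.8 = 48), not from session length.

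**The case for a change.** The best case for acting is that the flexibility clauses permit later adaptation but do not settle the starting plan. Both schedules are written as what will happen. A sleep coach working from the visit list, which separates aphasic participants elsewhere, could reasonably apply both longer calls to everyone. Because undelivered components are not logged as deviations, a gap between planned and delivered MET would not surface by that route. Clearer wording would cost almost nothing.

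Much of this stands. The documents do not say which text governs, and silence at Visits 13-14 is not an express exception. That justifies an editorial clarification, but it does not show harm to the study. Participants comment at Visit 17 on the sessions they received, so what was delivered matters more to the themes than the starting schedule. In a single-arm study that revises its intervention between batches, the schedule is expected to move. If aphasia were examined as a stroke-related factor for CPAP use, its MET would differ from that of other participants under either text, because those sessions are adapted by design. Settling the call schedule would not remove that limit on interpretation.

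**Conclusion.** The wording is inconsistent, but no change to the plan follows. The calls differ by 40-100 minutes between the two texts, and the sessions in the aphasia paragraph total 80-140 minutes against a 240-minute goal. These figures assume that sessions run within their stated lengths and that both in-person sessions take place; with only one, the total is 50-80 minutes. The shortfall counts as a conflict only if the goal covers aphasic participants and the list is complete, and neither is stated.

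This is a missing exception or cross-reference between a subgroup paragraph and an overview. The sponsor should reconcile the general MET text, the aphasia paragraph and Visits 9, 10 and 13-14, and decide which text changes; this review takes no position on that. The reconciliation would alter no endpoint, test, sample size, safety rule or conclusion.
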